10.2.2. Resource Utilization

Investigators will be asked to document the use of best supportive care measures, concomitant medications, transfusions, and disease/adverse event-related hospitalization days. Such assessments are to be taken throughout the Phase 2 portion of the study, through the 30-day short-term follow-up, and during the postdiscontinuation follow-up visit.

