10.3.1.1. Serious Adverse Events

An SAE is any adverse event from this study that results in 1 of the following outcomes:

- death
- a life-threatening experience (ie, immediate risk of dying)
- persistent or significant disability/incapacity

- initial or prolonged inpatient hospitalization
- congenital anomaly/birth defect
- considered significant by the investigator for any other reason.

Important medical events that may not result in death, be life-threatening, or require hospitalization may be considered serious adverse drug events when, based upon appropriate medical judgment, they may jeopardize the patient and may require medical or surgical intervention to prevent one of the outcomes listed in this definition.

SAE collection begins after the patient has signed informed consent and has received study drug. If a patient experiences an SAE after signing informed consent, but prior to receiving study drug, the event will not be reported as serious unless the investigator feels the event may have been caused by a protocol procedure.

Data on SAEs that occur before the end of trial will be stored in the collection database and the Lilly Safety System.

Study site personnel must alert Lilly or its designee of any **SAE** within 24 hours of investigator awareness of the event via a sponsor-approved method. If study site personnel contact Lilly or its designee by telephone regarding an SAE, study site personnel must also immediately provide official notification on study-specific SAE forms.

This 24-hour notification requirement refers to the initial SAE information and all follow-up SAE information.

Planned surgeries should not be reported as SAEs unless the underlying medical condition has worsened during the course of the study.

Planned hospitalizations or procedures for preexisting conditions that are already recorded in the patient's medical history at the time of study enrollment should not be considered SAEs. Hospitalization or prolongation of hospitalization without a precipitating clinical AE (eg, for the administration of study therapy or other protocol-required procedure) should not be considered SAEs.

SAEs due to disease relapse or progression, including death, should not be reported unless the investigator deems them to be possibly related to the study drug.

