12.1. Determination of Sample Size

Approximately 86 to 92 patients will be enrolled in this multicenter study.

In the Phase 1 portion of the study, the primary objective is to determine the MTD and the recommended dose for Phase 2. Approximately 13 to 16 patients will be enrolled into the adult (Part A), and approximately 13 to 16 patients will be enrolled in the pediatric (Part B) cohorts sequentially and without randomization to dose. The total sample size per cohort will be determined by DLTs.

In the Phase 2 portion of the study, the primary objective of this study is to compare the ORR (CR plus CRi) rate between LY3039478 administered with dexamethasone and placebo administered with dexamethasone, in adult patients with relapsed/refractory T-ALL/T-LBL. Approximately 60 evaluable patients will be randomized to the 2 treatment arms in a 2:1 ratio (40 randomized to LY3039478 and dexamethasone and 20 randomized to placebo and dexamethasone).

Assuming the ORR for the LY3039478 and dexamethasone arm is 40% and the ORR of the placebo and dexamethasone is 5%, the sample size of 60 evaluable patients will give approximately 82% statistical power to detect the difference, using a 2-sided Fisher's test at the significance level of 0.05, with 1 futility interim once the 30th enrolled patient completes the remission status determination (Section 12.2.14).

Primary analysis for ORR will be conducted once the last patient enrolled has completed 3 cycles of treatment, discontinued treatment, started new anticancer therapy or met criteria for objective progression. Patients who are randomized and do not achieve a CR or CRi will be considered as nonresponders in the primary analysis for ORR.

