Overall exposure to study drug, the numbers of patients completing each cycle, and the dose intensity will be summarized using descriptive statistics. The number of patients with any dose adjustment will be presented for entire treatment period as well as for each cycle. The number of patients with dose reductions, dose delays, or dose omissions will also be summarized, as will the reasons for dose adjustments.

An overall summary of AEs will be provided for AEs deemed by the investigator to be possibly related to study medication, and repeated for events regardless of study drug causality. Incidence rates of these events will be compared between treatment arms using Fisher's exact test.

A treatment-emergent AE (TEAE) is defined as an event that first occurred or worsened in severity after baseline.

The number of evaluable patients who experienced a TEAE, SAE, AE related to study drug, died, or discontinued from the study due to an AE will be summarized by treatment.

CTCAE v4.0 (or higher) will be used to report AEs by CTCAE terms.

Laboratory and nonlaboratory CTCAEs will be summarized by CTCAE term and maximum CTCAE grade, including the total for maximum Grade 3 and 4. These summaries will be provided for events regardless of study drug causality, and repeated for events deemed by the investigator to be possibly related to study medication.

MedDRA v16.1 (or higher) will be used when reporting AEs by MedDRA terms. The MedDRA lower level term will be used in the treatment-emergent computation. TEAEs will be summarized by SOC and by decreasing frequency of preferred term (PT) within SOC.

Reasons for death will be summarized separately for on-therapy and within 30 days of last dose of study drug/last visit. Serious adverse events will be summarized by PT.

Hospitalizations and transfusions during the study treatment period or during the 30-day short-term follow-up period will be summarized by treatment group.

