Abbreviations: CT = computed tomography; CTCAE = Common Terminology Criteria for Adverse Events; ECG = electrocardiogram; ECOG = Eastern Cooperative Group; FACT-Leu = Functional Assessment of Cancer Therapy-Leukemia; MRI = magnetic resonance imaging; PD = pharmacodynamic; PET-CT = positron emission tomography-computed tomography; PK = pharmacokinetic; T-ALL = T-cell acute lymphoblastic leukemia; T-LBL = T-cell lymphoblastic lymphoma.

- a LY3039478 is to be administered 3 days per week through each 28-day cycle. If assessments associated with a dose cannot be performed, the assessments may be performed either with the previous dose (if known in advance) or the next dose.
- b Per protocol Section 10.1.1. To be done for only those patients who had lesions at their baseline assessment.
- c For complete details, see [Attachment 3](#).
- d For central versus local labs refer to [Attachment 2](#).
- e Optional biopsy postdose, or at time of progression, or as clinically determined by investigator.
- f For confirmation of CR and when clinically indicated by investigator (timing as clinically indicated); per protocol Section 10.1.1.

Study Schedule, Protocol I6F-MC-JJCB: Phase 1 and 2 Follow-up Visits

		Initial Follow-up Visit ^a 801	Long-Term Follow-up Visits ^b 8XX	Notes
Physical Exam	Physical exam	X		
	Weight	X		
	Vital signs	X		Temperature, blood pressure, pulse rate
	Performance status	X		
	Hematology with manual differential ^c	X	X	For T-ALL patients who are in remission, CBC and platelets should be obtained every 1-3 months for the first 2 years and then every 3-6 months.
	Coagulation ^c	X		
	Serum chemistry ^c	X		
	CTCAE grading	X	X	
	Concomitant medications	X		
	FACT-Leu	X	X	Phase 2 only and patients in remission
	Resource utilization	X	X	Phase 2 only and patients in remission
Efficacy Measures	Patient survival status	X	X	
	Remission status	X	X	CT/MRI as clinically indicated every 2 -4 months For T-LBL patients followed by CT/MRI every 2 to 4 month as clinically indicated. For T-LBL patients followed by PET-CT only as clinically indicated.

Abbreviations: CBC = complete blood count; CT = computed tomography; CTCAE = Common Terminology Criteria for Adverse Events; FACT-Leu = Functional Assessment of Cancer Therapy-Leukemia; MRI = magnetic resonance imaging; PET = positron emission tomography;

T-ALL = T-cell acute lymphoblastic leukemia; T-LBL = T-cell lymphoblastic lymphoma.

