## 6.12. Health Outcomes/Quality-of-Life Analyses

### 6.12.1. Patient-Reported Outcomes

The FACT-Leu includes the 27-item cancer-specific Functional Assessment of Cancer Therapy-Leukemia-General (FACT-G) that assesses physical, social/family, emotional and functional well-being plus a 17-item subscale that assesses additional concerns specific to leukemia.

Methods for handling missing data, reverse scoring and other scoring guidelines are provided in [Appendix 1](#).

FACT-Leu results will be summarized descriptively by cycle and for postdiscontinuation visits, including number of completed questionnaires, compliance rates, reasons for noncompliance, scores for each scale, subscale and total scores, and changes from baseline.

Each of the 5 subscales, plus the Leukaemia trial outcome index, FACT-G total score and FACT-Leukaemia total score will be analysed by mixed effect model repeated measures. The model will include randomized treatment, cycle and the interaction of randomized treatment and cycle as fixed effects, with baseline and the interaction of baseline and cycle as a covariate. An unstructured variance covariance matrix will be used, provided data permit. Otherwise the following variance covariance structures will be tested and that with the best fit according to AIC selected: compound symmetry, heterogeneous Toeplitz, first-order autoregressive combined with random patient effect, heterogeneous autoregressive, or heterogeneous compound symmetry. The Kenward-Roger method will be used to estimate denominator degrees of freedom. Least square means and treatment comparisons with corresponding 95% confidence intervals (CIs) for each cycle will be presented in tabular and graphical displays.

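### The follow-up schedule collects post-treatment FACT-Leu and resource use only from patients in remission, which contradicts the plan's text on resource use and makes the post-discontinuation FACT-Leu summaries conditional on outcome

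*Protocol*

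**What the plan says.** **The schedule.** In the follow-up table of protocol Attachment 1, FACT-Leu and resource utilization are marked at Visit 801 (about 30 days after treatment ends) and at the long-term visits (8XX). Both rows carry the note "Phase 2 only and patients in remission". The note does not say whether remission means CR, CR or CRi, or also PR. At Visit 801 the physical examination, weight, vital signs, performance status, chemistry, coagulation and concomitant-medication rows have no such condition. Protocol 7.3.1 and 8.3 direct sites to this schedule.

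**Resource use.** Protocol 10.2.2, repeated in SAP 6.12.2, has investigators document supportive care, concomitant medications, transfusions and hospital days related to disease or adverse events, "through the 30-day short-term follow-up, and during the postdiscontinuation follow-up visit". Neither section mentions remission. Protocol 12.2.12 adds: "Hospitalizations and transfusions during the study treatment period or during the 30-day short-term follow-up period will be summarized by treatment group". That section works on the safety population, meaning everyone who received at least one dose.

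**FACT-Leu.** The synopsis has it completed at the start of every Phase 2 visit, while protocol 10.2.1 defers to the Study Schedule. On analysis, SAP 6.12.1 says "FACT-Leu results will be summarized descriptively by cycle and for postdiscontinuation visits", with completion counts and compliance rates. Protocol 12.2.11 says the same.

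**Other sources.** Protocol 9.6 requires concomitant medication and supportive care, which includes transfusions, to be documented at discontinuation and at the 30-day visit for all patients. For serious events, protocol 10.3.1.1 says "SAEs due to disease relapse or progression, including death, should not be reported unless" the investigator considers them possibly related to study drug.

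**The concern.** The instruction that sites work from and the text that the analysis relies on describe different patients. For resource use this is a direct contradiction. For FACT-Leu the body of the protocol defers to the schedule, so the difficulty is a mismatch with the synopsis and an unstated condition on the planned summaries.

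The condition matters because remission is determined after randomization and underlies the primary endpoint. By-arm figures restricted to patients in remission set unlike groups side by side, and under the design assumptions the groups also differ greatly in size. Treatment continues until progression or another discontinuation criterion (protocol 8.1). Anyone who stops for progression is outside the restricted group at Visit 801, although the schedule still has that patient examined there.

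At stake are the post-discontinuation part of the quality-of-life description and the 30-day hospitalization summary. Data not collected at Visit 801 may not be recoverable later.

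**Working it through.** **Inputs.** Protocol 12.1 gives the allocation as "40 randomized to LY3039478 and dexamethasone and 20 randomized to placebo and dexamethasone", assumed ORR (CR plus CRi) of 40% and 5%, and "approximately 82% statistical power to detect the difference, using a 2-sided Fisher's test at the significance level of 0.05".

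**1. The plan's own figure.** The continuity-corrected arcsine approximation to Fisher's test is

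power = Φ( 2[asin√(p1 − 1/(2n1)) − asin√(p2 + 1/(2n2))] × √(n1n2/(n1+n2)) − 1.960 ).

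With p1 − 1/80 = 0.3875 and p2 + 1/40 = 0.075, this is Φ(0.789 × 3.651 − 1.960) = Φ(0.921) = 82.2%, in line with the stated 82%. Exact enumeration gives 87.8%, or 87.7% with the futility stop applied, so the stated power is conservative. The point does not depend on it; the check confirms the inputs.

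**2. Expected remissions.** 40 × 0.40 = 16 and 20 × 0.05 = 1. By expectation, 24 of 40 (60%) and 19 of 20 (95%) never reach CR or CRi on randomized treatment.

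**3. Spread around those means (binomial).**
- 95% ranges: 10 to 22 and 0 to 3.
- P(more than 16 of 40) = 43%; P(more than 1 of 20) = 26%; P(at least one exceeded) = 58%.
- P(no control remission) = 0.95^20 = 36%.

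**4. Fewer may still be in remission at a post-treatment visit.** The documents give no share, so f is an assumption. Expected counts are 16f and 1f, and P(no control patient) = (1 − 0.05f)^20.

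| f | LY3039478 | Control | P(no control patient) |
|---|---|---|---|
| 25% | 4 | 0.25 | 78% |
| 50% | 8 | 0.5 | 60% |
| 75% | 12 | 0.75 | 47% |

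**5. More may qualify under a wider reading.** The duration-of-remission objective in protocol 6.2 counts PR. An assumed extra 5% to 20% PR in each arm gives 18 versus 2 up to 24 versus 5. Crossover can also add patients randomized to placebo: if all 19 expected control non-responders crossed over and remitted at an assumed 0% to 40%, that adds 0 to 7.6.

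**6. Precision.** The standard error of a difference in means, in SD units, is √(1/n1 + 1/n2). At 40 versus 20 it is 0.27 (95% half-width 0.54). At 16 versus 1 it is 1.03 (half-width 2.02).

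**7. Which items lack another source in patients not in remission.**

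| Item at 30 days | Another source for these patients? |
|---|---|
| Supportive care, concomitant medication | Yes: protocol 9.6 and the unrestricted row at Visit 801 |
| Transfusions | Largely: supportive care under 9.6; separate listing in SAP 6.10 |
| Hospital days from other adverse events | Through SAE reports, collected for 30 days (Table JJCB.10.2) |
| Hospital days from relapse or progression | None named apart from the resource-use record; such SAEs are excluded unless possibly drug-related |
| FACT-Leu | None |

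**The case against.** **The note may be meant only for the long-term visits.** One notes column serves both visit columns, and in the same table the hematology note on patients in remission describes an interval that fits only long-term follow-up. Read that way, the schedule would agree with protocol 10.2.2. This is possible, but Visit 801 is marked in the same rows and nothing tells a site that the condition does not apply there. An instruction open to both readings still has to be reconciled.

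**Sparing ill patients a 44-item questionnaire (27 + 17) is a legitimate choice.** This stands for the long-term visits. It does not explain restricting the resource-use record, which investigators complete, or leaving the resulting FACT-Leu summaries unlabelled.

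**Stronger conclusions that a reader might draw are not supported.**
- *That 16 and 1 are ceilings.* They are means, exceeded in at least one arm with 58% probability, and the qualifying group is wider if PR counts.
- *That planned between-arm tests are invalidated.* Post-discontinuation FACT-Leu is descriptive. The mixed-model comparisons are for each cycle, and the Fisher tests of resource use are by cycle and over all cycles (SAP 6.12.1 and 6.12.2). No test at Visit 801 or 8XX is specified.
- *That transfusions and supportive care go unrecorded.* Protocol 9.6 and the concomitant-medication row largely cover them.
- *That the quality-of-life objective fails.* FACT-Leu is collected at baseline and in the treatment cycles without regard to remission. Only the post-discontinuation part is affected.
- *That the arm with more remissions will appear to use more hospital care.* This could happen if uncollected days were counted as zero, but the documents do not say they would be.

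**Conclusion.** The point holds in a limited form. For resource use, Attachment 1 contradicts protocol 10.2.2 and SAP 6.12.2 and undercuts the 30-day hospitalization summary in protocol 12.2.12. For FACT-Leu, it fits badly with the synopsis and makes the descriptive post-discontinuation summaries in protocol 12.2.11 and SAP 6.12.1 conditional on remission without saying so. The items truly exposed are post-treatment FACT-Leu and disease-related hospital days in patients not in remission.

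The size rests on the design rates and on reading remission as CR or CRi on randomized treatment: about 16 versus 1 patients expected ever to qualify, with a 36% chance that the control arm supplies none. The number actually in remission at a post-treatment visit depends on a share the documents do not give; a definition that includes PR, or remissions after crossover, would raise the counts. The primary analysis, on-treatment FACT-Leu and the by-cycle comparisons are not touched. The consequence is confined to secondary descriptive outputs, but it is worth correcting before Phase 2 because correction is cheap.

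**What to change.** 1. In Attachment 1, change the Visit 801 note for resource utilization to *Phase 2 only, all patients*, to agree with protocol 10.2.2 and 12.2.12 and SAP 6.12.2.
2. Make the same change for FACT-Leu at Visit 801, to agree with the synopsis and support the summaries in SAP 6.12.1.
3. If the 8XX visits stay limited to remission, define the term (CR, CR or CRi, or also PR). State in SAP 6.12 that those summaries are conditional on remission and are not a comparison between arms.
4. Show placebo patients who have crossed over in the crossover group, as protocol 12.2.12 and SAP 6.14 already do for safety.

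The cost is one questionnaire and one form at a visit already scheduled, with no new visit or procedure. Some very ill patients will not complete FACT-Leu; the completion counts and compliance rates planned in SAP 6.12.1 will show how many.

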Attachment 2. Protocol I6F-MC-JJCB Clinical Laboratory Tests

Clinical Laboratory Tests

Hematology^{a,b} with manual differentiation:

Hemoglobin
Hematocrit
Erythrocyte count (RBC)
Mean cell volume (MCV)
Mean cell hemoglobin concentration (MCHC)
Leukocytes (WBC)
Neutrophils, segmented
Neutrophils, bands
Lymphocytes
Monocytes
Eosinophils
Basophils
Metamyelocytes
Myelocytes
Promyelocytes
Blasts
Atypical lymphocytes
Platelets
Nucleated RBCs (NRBC)/100 WBC
Reticulocytes

Urinalysis^{a,c}:

Specific gravity
pH
Protein
Glucose
Ketones
Blood
Urine leukocyte esterase

Immunophenotyping Lymphocyte panel in peripheral blood and bone marrow^a:

TdT, CD1a, CD2/3/4/5/7/8/11b/13/33/34/65/117,
cCD3, HLA-DR, % of lymphoblasts in bone marrow

Coagulation^b:

D-dimer
PTT
PT/INR
Fibrinogen
Antithrombin

Clinical Chemistry^{a,b}:

Serum Concentrations of:

Sodium
Potassium
Phosphorus
Magnesium
Chloride
Total bilirubin
Direct bilirubin
Alkaline phosphatase
Alanine aminotransferase (ALT)
Aspartate aminotransferase (AST)
Lactate dehydrogenase (LDH)
Gamma-glutamyl (GGT)
Blood urea nitrogen (BUN) or blood urea
Creatinine
Uric acid
Calcium
Glucose, random
Albumin
Total protein
Lipase

Other:

Immunoglobulins G, A, and M (IgG, IgA, IgM)^{b,c}
High-sensitivity C-reactive protein (hsCRP)^{b,d}
HTLV^{b,c}

Pregnancy Test (females only)^{a,c}

Cerebrospinal Fluid^a

Leukocytes (WBC)
Lymphoblasts

ECG Chemistry^b

Lipase^e
Thyroid stimulating hormone (TSH)
Tri-iodothyronine (T3)
Thyroxine (T4)
Albumine
Glucose, random^e
Calcium

Bone Marrow^{a,b,f} with manual differentiation:	Sodium ^e
Aspirate	Potassium ^e
Core biopsy	Phosphorus ^e
	Magnesium ^e
	Serum creatinine ^e

Abbreviations: CBC = complete blood count; ECG = electrocardiogram; HTLV = Human T-cell leukemia virus type 1; M/E = myeloid/erythroid; PT/INR = international normalized ratio of prothrombin time; PTT = partial thromboplastin time; RBC = red blood cells; WBC = white blood cells.

a Local or investigator-designated laboratory.

b Assayed by Lilly-designated laboratory.

c Performed at baseline only.

d To be performed with each chemistry panel.

e Test not performed if both chemistry and ECG chemistry required at same time point. See [Attachment 3](#).

f Including Lilly-designated laboratory assessment of minimal residual disease (MRD) to confirm remission status.

**Attachment 3. Protocol I6F-MC-JJCB Pharmacokinetic,
Pharmacodynamic, CSF and ECG Sampling Schedule**

PK, PD, CSF, and ECG Sampling Schedule – Phase 1– Part A (Adult Patients)

PK Sample Number	Cycle	Day	PK Sampling Time for LY3039478 ^a	PK Sampling Time for Dexamethasone ^a	CSF Sampling Time for LY3039478 ^b	PD Sampling Time for A β (1-x)] ^c	PD Sampling Time for NICD and Gene Expression Analysis ^{d,e,f}	ECG and ECG Chemistry
1	1	1	Predose	Predose		Predose	Predose	Predose
2	1	1	1-2h	1-2h		1-2h		
3	1	1	3-4h	3-4h		3-4h		3-4h
4	1	1	6-8h	6-8h		6-8h	6-8h	
5	1	1	24-30h	24-30h		24-30h		24-30h
6	1	8	Predose				Predose	
7	1	8	1-2h		1-4h			
8	1	8	3-4h					
9	1	8	6-8h				6-8h	
10	1	8	24-30h					
11	2	1	Predose					Predose

Abbreviation: CSF = cerebrospinal fluid; ECG = electrocardiogram; NICD = Notch intracellular domain; PD = pharmacodynamic; PK = pharmacokinetic.

^a Samples of approximately 3 mL of whole blood will be collected for measurement of LY3039478 and dexamethasone on Cycle 1 Day 1 only. On other days, 2 mL of whole blood will be collected for measurement of LY3039478.

^b Optional and only for Phase 1 adult patients.

^c Samples of approximately 3 mL of whole blood will be collected.

^d For the NICD ELISA, approximately 8 mL of whole blood will be collected in sodium citrate CPT tubes.

^e For the gene expression analysis, approximately 2.5 mL of whole blood will be collected.

^f NICD collection will be performed at select sites only.

Note: Collection of PD samples, where similar intervals are presented, should be collected the same time as PK samples. Collection of CSF sample should be at the same time as either the 1-2h or 3-4h plasma PK sample.

PK, PD, and ECG Sampling Schedule – Phase 1- Part B (Pediatric Patients)

PK Sample Number	Cycle	Day	PK Sampling Time for LY3039478 ^a	PK Sampling Time for Dexamethasone ^a	PD Sampling Time for NICD and Gene Expression Analysis ^b	ECG and ECG Chemistry
1	1	1	Predose	Predose	Predose	Predose
2	1	1	1-3h	1-3h		1-3h
3	1	1	6-8h	6-8h	6-8h	6-8 h
4	1	8	Predose		Predose	Predose
5	1	8	1-3h		3h	

Abbreviation: ECG = electrocardiogram; NICD = Notch intracellular domain; PD = pharmacodynamic; PK = pharmacokinetic.

^a Samples of approximately 2 mL of whole blood will be collected for measurement of LY3039478 and dexamethasone (where assayed).

^b NICD collection will be performed at select sites only.

Note: Collection of PD samples, where similar intervals are presented, should be collected the same time as PK samples.

PK, PD, and ECG Sampling Schedule – Phase 2 (Approximately 30 Patients)

PK Sample Number	Cycle	Day	PK Sampling Time for LY3039478/ Placebo ^b	PK Sampling Time for Dexamethasone ^b	PD Sampling Time for NICD and Gene Expression ^c	ECG ^a and ECG Chemistry
1	1	1	Predose	Predose	Predose	Predose
2	1	1	1-3h	1-3h		1-3h
3	1	1	6-8h	6-8h	6-8h	
4	1	15	Predose	Predose		
5	1	15	1-3h	1-3h		
6	1	15	6-8h	6-8h		
7	2	1	Predose			Predose

Abbreviation: ECG = electrocardiogram; NICD = Notch intracellular domain; PD = pharmacodynamic; PK = pharmacokinetic.

a ECG required for all patients.

b Samples of approximately 3 mL of whole blood will be collected for measurement of LY3039478 and dexamethasone in Cycle 1 only. On other days, 2 mL of whole blood will be collected for measurement of LY3039478.

c NICD collection will be performed at select sites only.

Note: Collection of PD samples, where similar intervals are presented, should be collected the same time as PK samples.

